## 8.4 Reporting Procedures

## 8.5 Adverse Event Reporting

All AEs including those of Special Interest, *regardless of relatedness to the study drug*, must be fully and completely documented on the AE eCRF and in the subject's medical notes. The following attributes must be assigned: event description, dates and times of onset and resolution, clinician's assessment of severity, assessment of relatedness to study drug (either related or not related), and action taken. The Investigator may be asked to provide additional follow-up information.

In the event that a subject is withdrawn from the study because of an AE, it must be recorded on the eCRF. The subject must be followed and treated by the Investigator until the AE has resolved, stabilized, or a new chronic baseline has been established.

The Investigator must report all observed AEs and all reported AEs. At each visit the Investigator will ask the subject a nonspecific question (e.g., "Have you noticed anything different since your last visit?") to assess whether any AEs have been experienced since the last report or visit. AEs will be identified and documented on the AE page of the eCRF in appropriate medical terminology. The severity and the relationship to the study drug will be determined and reported on the eCRF (see [Sections 8.1.1](#) and [8.2.2](#)).

Note that any intermittent or as-needed ("PRN") use of medication (and specifically any newly prescribed medication) during the course of a study may indicate the occurrence of an AE that may need to be recorded on both the AE page of the eCRF and the Concomitant Medication page.

### 8.5.1 Serious Adverse Event Reporting

The reporting of SAEs by Sponsor to the Regulatory Authorities is a regulatory requirement. Each Regulatory Authority has established a timetable for reporting SAEs based upon established criteria. It is the responsibility of the principal Investigator to report SAEs to the Sponsor within 24 hours.

All SAEs must be reported immediately (within 24 hours of discovery) to the Medical Monitor or designee. **Do not** delay in the reporting of a suspected SAE in order to obtain additional information. Any additional information, if collected, can be reported to the Sponsor as a follow-up to the initial report. SAEs will be reported using the SAE forms provided. Please remember to give details of the patient identification number or other appropriate terminology and ensure the narrative is comprehensive and includes a chronology and assessment of the event.

At a minimum, events identified by Bonti to require expedited reporting as serious, unexpected, and possibly related to study drug must be brought to the attention of the responsible IRB/IEC. For EU member States, Bonti or designee will provide reports of suspected unexpected serious adverse reactions (SUSARs) directly to the IECs, as required by local legislation. In all other countries, it is the Investigator's responsibility to provide these expedited reports to the responsible IRB/IEC. It is also the Investigator's responsibility to notify the responsible IRB/IEC regarding any new and significant safety information.

The process for reporting an SAE or study drug overdose is as follows:

- Complete an AE eCRF page.
- Complete an SAE form—this must include the patient identification number.
- Complete the narrative, which should be comprehensive and include a chronological description and assessment of the event.
- Complete the cover sheet.
- Call the Medical Monitor or designee for life-threatening or fatal events (see details that follow).
- Include results of any related laboratory tests or investigations, histopathologic examinations, or consultations with other healthcare professionals that serve to clarify the nature of the event, the cause of the event, or both.
- Email the cover sheet and the SAE form (within 24 hours of discovery) to the Medical Monitor or designee (see details that follow).

Follow-up information on a previously reported SAE should be processed using a new SAE form. Follow-up information includes additions, deletions, and corrections to the initial report. Previously signed, dated, and emailed forms should not be altered to provide follow-up SAE information of any type. The following must be done when providing follow-up information:

- Mark the box that indicates follow-up information is being provided.
- Fill out the dates on each page of the form that indicates this is a follow-up report.
- Restate the event as it appears on the initial report. If the event has changed, indicate, with parentheses, what the event was previously per the example below:

SERIOUS ADVERSE EVENT	Myocardial Infarction
Diagnosis or Sign/Symptom	(previously chest pain)

All SAEs must be reported immediately (within 24 hours of discovery) by email to the Medical Monitor or designee. Calls related to SAEs should first be directed to the Medical Monitor or designee.

Bonti or designee will provide the Investigator with alternative contact information if the Medical Monitor will not be available.

These events will be reported within 24 hours of discovery, particularly for life-threatening or fatal events, and the Investigator should continue to provide reports to the IRB/IEC, as required. In the event of any SAE (other than death), the patient will be instructed to contact the Investigator (or Medical Monitor or designee) using the telephone number provided in the ICF. All subjects experiencing an SAE will be seen by the Investigator or designee as soon as is feasible following the report of the SAE.

All SAEs will continue to be followed until the end of the Study or until such events have resolved or the Investigator, in conjunction with the Sponsor, deems them to be chronic or stable.

SAEs occurring up to 30 days after the study follow up period should be reported if in the judgement of the Investigator there is "a reasonable possibility" that the event may have been caused by the product.

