### 8.1.2 Definition of Serious Adverse Events (SAE)

In addition to the severity rating, each AE is to be classified by the Investigator as "serious" or "not serious." The seriousness of an event is defined according to the applicable

regulations and generally refers to the outcome of an event. A serious adverse event (SAE) is one that meets one or more of the following:

- Is fatal
- Is immediately life-threatening
- Is permanently (or significantly) disabling
- Requires hospitalization
- Prolongs existing hospitalization
- Is a congenital anomaly or birth defect (in an offspring)
- Is judged medically significant

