## **8.3 Time Period and Frequency for Event Assessment and Follow-up**

The occurrence of an AE or SAE may come to the attention of study personnel during study visits and interviews of a study participant presenting for medical care, or upon review by a study monitor. All AEs including local and systemic reactions not meeting the criteria for SAEs will be captured on the appropriate eCRF. Information to be collected includes event description, dates and times of onset and resolution, clinician’s assessment of severity, assessment of relatedness to study drug (assessed only by those with the training and authority to make a diagnosis), and action taken. All AEs occurring while on study must be documented appropriately regardless of relationship. All AEs will be followed to adequate resolution.

Any medical condition that is present at the time that the participant is screened will be considered as baseline and not reported as an AE. However, if the study participant’s condition deteriorates at any time during the study, it will be recorded as an AE. UPs will be recorded in the data collection system throughout the study.

Changes in the severity of an AE will be documented to allow an assessment of the duration of the event at each level of severity to be performed. AEs characterized as intermittent require documentation of onset and duration of each episode.

The Investigator will record all reportable events with start dates occurring any time after informed consent is obtained until the AE has resolved, stabilized, or a new chronic baseline has been established. At each study visit, the Investigator will inquire about the occurrence of AE/SAEs since the last visit. Events will be followed for outcome information until resolution or stabilization.

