- Baseline value is defined as the last valid measurement prior to the start treatment administration.
- Change from baseline is defined as post-baseline value minus baseline value.
- Duration of an AE will be computed in hours in the first 96 hours during confinement and thereafter in days as the stop date of the event minus the start date plus 1. If reported as ongoing at the time of database lock, the stop date will be imputed as the date of the last visit or the last date of any AE for the subject in the database, whichever is later. Other missing dates will be imputed as described in [Table 8-1](#).
- The number of days in the study is computed as: [Date of study completion or withdrawal minus the date of treatment administration (Day 0)] + 1.
- If duplicate values are obtained at a given visit (e.g., repeated vital sign measurements), the last value will be used unless it is noted that the measurement was in error for that value. Values that compromise interpretation will not be used in summaries (e.g., values

that were obtained post-dose will not be summarized as pre-dose values).

- If a pre-rescue NPRS is recorded in the same minute as a rescue medication is recorded, the NPRS will be assumed to have occurred PRIOR to the administration of rescue.
 - If a subject experiences inadequate analgesic relief and takes non- protocol specified rescue medication, they will be treated as 'discontinued' from the efficacy portion of the study. The date/time of the discontinuation will be assumed to be the date/time of the start of non-protocol specified rescue captured on protocol deviations eCRF. Early discontinuation from the efficacy portion affects the computation of the analgesic endpoints only.

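### Serious adverse events fall under two follow-up rules with different stopping points, and the SAP gives events still open at database lock a duration that looks complete

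*Protocol*

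**What the plan says.** Protocol 8.5.1 gives three stops for SAE follow-up, joined as alternatives. The first two are in "All SAEs will continue to be followed until the end of the Study or until such events have resolved". The third applies when "the Investigator, in conjunction with the Sponsor, deems them to be chronic or stable".

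Protocol 8.3 states its rule twice, with no calendar stop either time: "All AEs will be followed to adequate resolution" and "Events will be followed for outcome information until resolution or stabilization". Its opening words, "The occurrence of an AE or SAE may come to the attention of study personnel", show that it covers serious events. Protocol 8.1.2 points the same way, because there "each AE is to be classified by the Investigator as" serious or not serious, which makes SAEs a class of AE.

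Protocol 8.5 also has an open-ended rule (resolved, stabilised or new chronic baseline). It follows directly on the sentence "In the event that a subject is withdrawn from the study because of an AE, it must be recorded on the eCRF", so it concerns subjects withdrawn for an AE and not every AE.

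Protocol 8.5.1 also asks for reports of SAEs that arise up to 30 days after the follow-up period, if the investigator sees a reasonable possibility that the product caused them.

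For an AE ongoing at database lock, SAP 3 says that "the stop date will be imputed as the date of the last visit or the last date of any AE" for that subject, whichever is later. After the first 96 hours, duration is counted in days as stop date minus start date plus 1.

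**The concern.** A site looking for SAE instructions will go to 8.5.1. There it may read that follow-up of an unresolved, unstable serious event can end with the study. In doing so it would comply with 8.5.1 and breach 8.3. Safety and tolerability is a stated objective, and Protocol 8.8 foresees a possibly prolonged course of respiratory compromise. The outcomes most exposed to an early stop are those of the longest events.

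The SAP convention adds a second, independent problem. An event with no observed end is given a stop date and a finite duration, and in a duration column it then looks like one that resolved. If sites apply the 8.5.1 stop, more events will still be marked ongoing at lock and the convention will be used more often.

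**Working it through.** The plan states no figure to reproduce. The check compares the texts and adds two short calculations.

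**Follow-up stops side by side**

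| Section | Covers | Outcome stop | Calendar stop |
|---|---|---|---|
| Protocol 8.3 | all AEs, SAEs included | resolution or stabilisation | none |
| Protocol 8.5 | subjects withdrawn for an AE | resolution, stabilisation or new chronic baseline | none |
| Protocol 8.5.1 | SAEs | resolution, or deemed chronic or stable | end of the study |

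The outcome stops are of the same kind in all three. Only 8.5.1 has a calendar stop, and no sentence gives precedence to 8.3 or to 8.5.1.

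**What the end of the study means**

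- Protocol 6.1.9 places the End of Study Visit on Day 29. On that reading, and under 8.5.1 alone, an SAE starting on Day s has 29 - s further days of required follow-up. A start on Day 15 leaves 29 - 15 = 14 days, and a start on Day 29 leaves 0.
- Protocol 13.4.1, on sample storage, ties the end of the study to the writing of the final study report. On that reading the calendar stop comes much later and the gap is small.

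**The 30-day reporting window**

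If follow-up ends on Day 29, the window runs from Day 30 to Day 29 + 30 = Day 59. On the Day 29 reading, every SAE in that window begins after the 8.5.1 stop, and 8.5.1 gives no follow-up rule for it.

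**The SAP convention**

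Recorded duration = max(last visit, last AE date) - start + 1.

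For an event starting on Day 25 and still open at lock, with a Day 29 last visit and no later AE date, this is 29 - 25 + 1 = 5 days, however long the event truly lasts. A later AE date raises the figure, but that date is already in the database and so cannot fall after lock. An event truly open at lock ends after lock. The recorded duration is therefore too short for every such event, serious or not.

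**The case against.** The strongest reply is that nothing is lost if a site obeys both sections. Section 8.3 already binds SAEs, including those open at Day 29. That is right, and it rules out a tempting stronger reading, namely that serious events simply have a weaker rule than minor ones. They have two rules in conflict. It is equally wrong to cite 8.5 as a requirement for every AE, given its scope. The conflict remains, because a site can also comply with 8.5.1 alone.

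The second reply is that the only express definition of the end of the study is the final report. It stands in a parenthesis about stored samples, while the Day 29 wording describes a visit. Neither settles 8.5.1, so the 0 to 14 days above is conditional on the Day 29 reading.

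On the SAP, the convention applies only to events open at lock and takes the later of two dates. An event that starts on Day 25, is followed as 8.3 requires and ends before lock keeps its real stop date. The convention also applies to all AEs, so it is not evidence of a problem specific to SAEs. The public SAP does not show its AE section, so it cannot be seen whether durations are summarised or only listed.

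Two further inferences fail. With four active subjects in each of Cohorts 1 to 4, one event is 1/4 = 25% of a dose group. That is an incidence share, and the follow-up stop does not change it. The 2-4 weeks in Protocol 2.2.1 is the expected duration of efficacy. For systemic toxicity, the text after Protocol Table 3 expects recovery to begin about 1 week after dosing, so 2-4 weeks does not measure how long a toxic event would last.

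**Conclusion.** The point holds as an unresolved conflict between Protocol 8.3 and 8.5.1 over when SAE follow-up may stop, together with a separate SAP convention that shortens the duration of events still open at lock.

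The size of the protocol gap cannot be fixed from the documents. It is material on the Day 29 reading and small on the final-report reading. The SAP effect does not depend on that choice. Its direction is certain for any event truly open at lock; its amount depends on how long the event goes on after the imputed date. If an event is marked ongoing only because follow-up stopped, its true end is unknown and the imputed date is still not an observed one.

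The effect is confined to the completeness of SAE outcomes and to AE durations. Incidence counts, the primary endpoint and the sample size are untouched. SAP 1 plans descriptive summaries only, after early termination.

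**What to change.** **Protocol.** Reconcile 8.3, 8.5 and 8.5.1 so that one stated stop applies to SAE follow-up. Define the end of the study where that term is used. State that the rule also covers SAEs reported in the 30 days after the follow-up period. Which stop is adopted is for the sponsor and investigators to decide; what matters here is that there is only one.

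**SAP 3.** Do not impute a stop date for AEs ongoing at lock. Report them as ongoing, with duration treated as censored (at least X days, counted to the last date on which the event was known to be open). Do not drop them from duration summaries, because that would remove the longest events.

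**Cost.** A few sentences in the protocol, one in the SAP and a slightly longer footnote to the AE table. If the open-ended stop is kept, there will be occasional site contact after Day 29, which 8.3 already requires.

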### **8.5.2 Reporting of Pregnancy**

Females that may be able to get pregnant will be required to take pregnancy test before study agent administration. The results of the pregnancy testing must be negative in order to be in the study.

All female subjects who may be able to get pregnant must agree to use either a highly effective method of contraception with failures rates less than 1% per year or dual methods of contraception with overall failures rates less than 1% per year from the day of dosing until 3 months afterwards. Female subjects who underwent sterilization must have initiated the procedure at least 3 months prior to the day of dosing. Female subjects using oral contraception must have initiated treatment at least 2 months prior to the day of dosing.

In the event that a female subject does become pregnant at any time during the study, the Investigator must notify the Medical Monitor or designee within 48 hours of learning about the pregnancy.

The Investigator will be required to complete the Pregnancy Report/Outcome Form and any additional documents provided by the Sponsor, follow the subject through the pregnancy term, and report to the Medical Monitor or designee the course of the pregnancy, including perinatal or neonatal outcome.

Information on the status of the mother and the child will be forwarded to the Medical Monitor or designee using the Pregnancy Report/Outcome Form. Any premature termination of the pregnancy will also be reported on this form.

Although pregnancy occurring in a clinical study is not considered to be an SAE, any pregnancy complication or elective termination of a pregnancy for medical reasons will be recorded as an AE and will be followed as such. A spontaneous abortion is considered to be an SAE.

## **8.6 Study Halting Rules**

See [Section 4.1.1](#).

## **8.7 Safety Oversight**

The study SRC including the Investigators, Medical Monitor, Study Director as well as other *ad hoc* representatives as appropriate will regularly monitor all aspects of patient safety throughout this study. The SRC will review all available data in a blinded manner (may include: vital signs, ECGs clinical laboratory tests, incidence of SAE and TEAE) to assess the safety of each dose level of EB-001 prior to escalating to the next dose level.

## **8.8 Risk Management of Prolonged Respiratory Compromise**

Subjects may develop adverse effects indicative of spread of toxin, including a potentially prolonged course of respiratory compromise. If there were to be a significant respiratory event, the study site is located inside an acute care hospital. All subjects have access 24/7 to a fully-functional code blue team (including personnel expert in managing airways and respiratory emergencies). In addition, the study site is located 100 yards from the hospital emergency room so subjects can be quickly and easily transferred after stabilization by the code team.

If there is any significant respiratory event in the study i.e., profound hypoxia, respiratory depression, sedation etc., the study site and staff will follow usual standard of care which may include verbal and physical stimulation, high flow oxygen via face mask or big-mask, airway management, and calling for the hospital code team for immediate transfer to the emergency room once stabilized, if required. Subjects who do not respond to these measures may require endotracheal intubation and mechanical ventilation. Opiate reversal agents may be used in subjects who received opioid rescue medications.

In addition, systemic toxicity of EB-001 may be treated with a multi-valent anti-toxin.

## 9 CLINICAL MONITORING AND COMPLIANCE

The Sponsor representatives and regulatory authority inspectors are responsible for contacting and visiting the Investigator for the purpose of inspecting the facilities and, upon request, inspecting the various records of the study (e.g., eCRFs and other pertinent data), provided that subject confidentiality is respected.

The study monitor is responsible for inspecting the eCRFs at regular intervals throughout the study to verify the following: adherence to the protocol; completeness, accuracy, and consistency of the data; and adherence to local regulations on the conduct of clinical research. The monitor should have access to subject medical records and other study-related records needed to verify the entries on the eCRFs. The Investigator must agree to cooperate with the monitor to ensure that any problems detected in the course of these monitoring visits are resolved.

In accordance with ICH Good Clinical Practice (GCP) and the Sponsor audit plans, this study may be selected for an audit. Inspection of site facilities (e.g., pharmacy, drug storage areas, laboratories, etc.) and review of study-related records may occur in order to evaluate the trial conduct and compliance with the protocol, ICH GCP, and applicable regulatory requirements.

A separate clinical monitoring plan (CMP) will describe in detail who will conduct the monitoring, at what frequency monitoring will be done, at what level of detail monitoring will be performed, and the distribution of monitoring reports. A CMP ordinarily should focus on preventing or mitigating important and likely risks, identified by a risk assessment, to critical data and processes. The types (e.g., on-site, centralized), frequency (e.g., early, for initial assessment and training versus throughout the study), and extent (e.g., comprehensive (100% data verification) versus targeted or random review of certain data (less than 100% data verification)) of monitoring activities will depend on a range of factors, considered during the risk assessment, including the complexity of the study design, types of study endpoints, clinical complexity of the study population, geography, relative experience of the PI and of the Sponsor with the PI, electronic data capture, relative safety of the study agent, stage of the study, and quantity of data.

